5.1.2 Additional study treatment

No additional treatment beyond investigational treatment is requested for this trial. Nevertheless, all randomized patients will be required to receive standard of care background HF management during both the index hospitalization and post discharge, according to local guidelines/international standards. This treatment post-randomization can include but is not limited to intravenous and/or oral diuretics, angiotensin-converting enzyme (ACE) inhibitors/angiotensin receptor antagonists, β blockers and aldosterone receptor antagonists, etc.

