5.5 Treating the patient

5.5.1 Patient numbering

Each patient is uniquely identified by a Subject Number which is composed by the site number assigned by Novartis and a sequential number assigned by the investigator. Once assigned to a patient, the Subject Number will not be reused.

Upon signing the informed consent form, the patient is assigned the next sequential number by the investigator. The investigator or his/her staff will contact the IRT and provide the requested identifying information for the patient to register them into the IRT. The assigned patient number should be entered in the field labeled “Subject ID” on the electronic Case Report Form (eCRF) data entry screen.

If a patient correctly randomized fails to be treated for any reason, the IRT must be notified immediately that the patient was not treated. The patient will be followed up to Day 30 and relevant information, together with the reason for not being treated, will be entered into the eCRF.

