5.5.5 Permitted dose adjustments and interruptions of study treatment

Systolic Blood Pressure (SBP) has to be ≥ 125 mmHg for the patient to be eligible, and then ≥ 125 mmHg during the screening period, in particular at the end of the screening period just before calling the IRT for randomization. In many centers, continuous cardiac monitoring will probably be applied and this will keep the site informed about SBP values.

Considering the high fluctuation of blood pressure in patients with decompensated HF, especially because the patient might be under the effect of nitrates (even at low dose) and diuretics, it is advised to minimize the time windows between the end of screening, the IRT call and start of the serelaxin infusion.

In practice:

- BP has to be measured at the end of screening and SBP must be ≥ 125 mmHg before calling the IRT. Once the patient is randomized, the study drug should be prepared promptly (if the patient is in the serelaxin group).
- Just before the immediate start of study drug infusion, SBP must be assessed again. During that interval between randomization and infusion start, sometime will elapse (30 to 60 minutes in most cases) and BP may fluctuate.
 - It is not required that pre-infusion SBP be ≥ 125 mmHg (SBP ≥ 125 mmHg is an inclusion criterion and matters only up to randomization)
 - If at the immediate start of study drug infusion, SBP is below 100 mmHg (SBP < 100 mmHg), serelaxin should not be started, neither now nor later. The patient will remain in the study up to 30 days but will not have received serelaxin
 - If a blood pressure fall has occurred since randomization but SBP is still ≥ 100 mmHg, the decision to start or not the infusion remains at the discretion of the investigator, based on the hemodynamic context of the patient (i.e. previous hemodynamic stability, DBP, concomitant medications, medical response to IV furosemide/diuretics, etc.).

Of note, there is no mandatory time window between randomization and start of the study drug infusion. This time span should be kept as short as possible. For microbiological reasons, there is a maximum time of 4 hours allowed between preparation (mixing) of the study drug and infusion start.

If at any time during the study drug infusion, the subject's systolic blood pressure decreases by >40 mm Hg from just before the study drug infusion but is ≥ 100 mmHg in two consecutive measurements 15 min apart, the serelaxin infusion rate will be decreased by 50% for the

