9.1.4 Safety population

The safety population will include all patients who received any amount of study treatment or standard of care treatment and who have at least one post-baseline safety assessment. Of note, the statement that a patient had no adverse events also constitutes a safety assessment. Patients will be analyzed according to treatment received. The analyses on safety parameters will be conducted in the Safety set.

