3. POPULATIONS OF ANALYSIS

Analysis population

Patients without a valid or adequately obtained Informed Consent Form (ICF) will be excluded from any analysis population.

The following analysis populations are defined:

- **Screened set (SCR):** all patients who signed the informed consent.
- **Randomized set (RAN):** all patients who received a randomization number, regardless of receiving trial medication and including mis-randomized patients.
- **Full analysis set (FAS):** all randomized patients who were not mis-randomized. Following the intent-to-treat (ITT) principle, patients will be analyzed according to the treatment they have been assigned to at randomization. Mis-randomized patients are those who have not qualified for randomization, have been inadvertently randomized into the study but who did not enter the treatment phase and who did not receive serelaxin. Mis-randomized patients are defined as cases where randomizations were made by the site either prematurely or inappropriately prior to confirmation of the patient's final randomization eligibility. These patients should subsequently be discontinued from the study.
- **Per Protocol set (PP):** all patients in the FAS without major protocol deviations, as defined in the Patient Validation Document (PWD).
- **Safety set (SAF):** all patients who received any amount of study treatment or standard of care treatment and who have at least one post-baseline safety assessment. Of note, the statement that a patient had no adverse events also constitutes a safety assessment. Patients will be analyzed according to treatment received.

Protocol deviation

The protocol deviation concerning the mis-randomization will be detected during the course of the study and reported by means of the specific tool developed on eCRF.

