	Subject not randomized but entered the treatment phase	PROC06		X	X	X	
	Subject mis-randomized (i.e. subject who has not been qualified for randomization, has been inadvertently randomized into the study, who did not enter the treatment phase and who did not undergo Serelaxin administration)	PROC07			X	X	X

* Deviations codes as defined in the Protocol Deviation Handling Document (blind & unblind). Codes could possibly change before database lock.

In addition, deviations not defined in the protocol resulting in exclusion of subjects from an analysis population are outlined in the table below.

Table 3-2: Non-protocol deviations resulting in exclusion of subjects from analysis populations

Category	Description	Non-Protocol Deviation	Exclusion from analysis set				
			SCR	RAN	FAS	PP	SAF
Non-protocol deviation	Subject has no post-baseline safety assessment.						X

	Statistical Analysis Plan
	Sponsor: NOVARTIS Protocol number: CRLX030A3301

Category	Description	Exclusion from analysis set				
		SCR	RAN	FAS	PP	SAF
Non-protocol deviation	Subject randomized to Serelaxin group but not receiving any dose of study medication				X	X

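### SAP Table 3-2 drops never-infused serelaxin patients from a safety set whose definition admits them; separately, treatment-emergent events start at different points in the two arms (minor)

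*SAP*

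**What the plan says.** **Membership.** SAP section 3 defines the safety set as "all patients who received any amount of study treatment or standard of care treatment and who have at least one post-baseline safety assessment", and adds: "Patients will be analyzed according to treatment received". Protocol 9.1.4 has the same rule: "The safety population will include all patients who received any amount of study treatment or standard of care treatment".

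**Background care and follow-up.** Protocol 5.1.2 states that "all randomized patients will be required to receive standard of care background HF management during both the index hospitalization and post discharge". Under Protocol 5.5.1, a correctly randomized patient who is not treated is "followed up to Day 30 and relevant information, together with the reason for not being treated, will be entered into the eCRF". Protocol 5.5.5 describes one route to being never infused, systolic pressure below 100 mmHg when the infusion is due to start: "The patient will remain in the study up to 30 days but will not have received serelaxin".

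**Exclusion.** SAP Table 3-2 lists, among deviations that the protocol does not define, "Subject randomized to Serelaxin group but not receiving any dose of study medication", with marks under the per-protocol and safety columns. Table 3-1 (code DRUG14) already covers undosed patients whose pre-infusion systolic pressure was at least 100 mmHg. The Table 3-2 row has no pressure condition.

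**Time origin.** Under SAP 5.3, treatment-emergent events begin at treatment initiation for serelaxin and at randomization for standard of care (SOC). Events between consent and treatment initiation are listed separately. Protocol 9.5.2 sets the same origins for incident events. Protocol 5.5.5 gives a usual gap of 30 to 60 minutes but says that "there is no mandatory time window between randomization and start of the study drug infusion".

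**The concern.** The definition and the table give different answers for the same patient. Read literally, the definition keeps a never-infused serelaxin patient and the as-treated rule puts that patient in the SOC column. Table 3-2 puts the patient in neither column.

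The exclusion is made after randomization and can act only in the serelaxin arm. It takes in patients who were not started because of low blood pressure, while comparable SOC patients stay in. Protocol 6.5 assesses safety by comparing the arms, and SAP Table 5.3-1 names hypotension as the identified risk.

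The time-origin rule is a different kind of problem. Both documents pre-specify it and it contradicts nothing. It does mean that an event shortly after randomization enters the SOC treatment-emergent tables, while the same event before infusion enters only a listing for serelaxin.

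**Working it through.** **Step 1: set the texts side by side.**

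| Source | Where a never-infused serelaxin patient goes |
|---|---|
| SAP section 3 and Protocol 9.1.4, definition with as-treated rule | In the safety set, SOC column |
| SAP Table 3-2 | Not in the safety set |
| SAP 5.1, post-baseline phase | Has a safety phase, starting at randomization |
| SAP 5.1, investigational treatment | Serelaxin-arm summary of treatment given (yes/no), with reason if not, in the safety set as well as the full analysis set (FAS) |
| SAP 5.1, discordant-treatment listing | Safety set only, both arms |

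Under Table 3-2 the "no" category of that summary would be empty in the safety set, and the listing could contain no serelaxin-randomized patient. The two marks in the Table 3-2 row align with the per-protocol and safety columns. Reading them as FAS and per-protocol would contradict the FAS definition, which removes only mis-randomized patients. The column positions for DRUG14 in Table 3-1 cannot be read reliably.

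**Step 2: inputs.** From the documents: 3,183 patients at 2:1, so 3,183 × 2/3 = 2,122 serelaxin and 3,183 / 3 = 1,061 SOC. The documents give no never-infused share and no hypotension rate, and the sample-size text is redacted, so there is no figure of the plan's own to reproduce. Assumptions: hypotension p = 5% in both arms by randomized arm; share never infused s = 0.5% to 2% (about 11 to 42 patients); risk among them q = 0% to 20%.

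**Step 3: effect of the Table 3-2 exclusion.** The remaining serelaxin rate is (p − s·q)/(1 − s). The shift is therefore s(p − q)/(1 − s), and its sign depends only on whether q is below or above p.

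| s | q = 0% | q = 5% | q = 20% |
|---|---|---|---|
| 0.5% | +0.03 points | 0 | −0.08 |
| 1% | +0.05 | 0 | −0.15 |
| 2% | +0.10 | 0 | −0.31 |

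Example: s = 2%, q = 20% gives (0.050 − 0.004)/0.98 = 4.69%, a shift of −0.31. With q = 0 it is 0.050/0.98 = 5.10%, a shift of +0.10. At s = 1% and q = 20% the shift is −0.18 if p = 2% and −0.10 if p = 10%.

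**Step 4: the literal definition instead.** If these patients move to SOC, that rate becomes (0.05 + 2s·q)/(1 + 2s), because the serelaxin arm is twice the size of the SOC arm. At s = 1%, q = 20%: 0.054/1.02 = 5.29%, against 4.85% for serelaxin, a difference of −0.45. At s = 2%, q = 20%: 0.058/1.04 = 5.58%, against 4.69%, a difference of −0.88.

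**Step 5: time origin, dosed patients.** With gap g and onset spread evenly over H hours, a fraction g/H of serelaxin events falls outside the treatment-emergent tables, and the shift is −p·g/H. About 2,122 × 0.05 = 106 events are expected.

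| H | g = 0.5 h | g = 1 h |
|---|---|---|
| 120 h | 0.44 events, −0.02 points | 0.88 events, −0.04 |
| 48 h | 1.11 events, −0.05 | 2.21 events, −0.10 |

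For a given g/H these are upper values, because they assume that no patient with an event in the gap has a later one. The gap has no stated maximum. An assumed 4 hours over 120 hours would give 0.05 × 4/120, or −0.17 points.

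**The case against.** The strongest reply is that the SAP settles the matter. Section 3 says that certain deviations may lead to exclusion from analysis sets, Table 3-2 names this case, and a programmer would follow the table. The words on study treatment or standard of care can also be read by arm, since standard of care alone is the comparator. On that reading the definition never admitted these patients. The by-arm reading is possible, but it does not reconcile the SAP 5.1 text set out above, so a clarification is still needed.

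The reply is right that Table 3-2 does less harm than the literal definition: −0.15 against −0.45 points at 1% never infused and 20% risk. A reader might take the −0.88 figure as the cost of Table 3-2. It is not; it is the result that Table 3-2 avoids.

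A reader might also infer that the exclusion makes serelaxin look safer. The documents do not support a direction. The exclusion removes denominators as well as events, and patients left undosed for administrative reasons may carry little recorded risk. Closer monitoring pulls the other way: Protocol 6.5.2 schedules eight pressure readings for serelaxin from pre-infusion to 6 hours, and one for SOC at 6 hours, which tends to raise recorded hypotension under serelaxin.

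Starting treatment-emergent events at first dose is a defensible convention, since an event before infusion cannot be a drug effect. Some of the gap is also covered elsewhere. SAP 5.1 reports reasons for exclusion from each set and, in the FAS, treatment given or not. SAP 5.3 lists all deaths. The dedicated blood-pressure-decrease analysis is confined to serelaxin during administration, so never-infused patients do not affect it. None of this gives a comparative adverse-event table that keeps these patients in their randomized arm.

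**Conclusion.** The mismatch between the safety-set definition and Table 3-2 is real, and the exclusion acts in one arm only. The unequal treatment-emergent start is a pre-specified comparability weakness and not an inconsistency.

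The combined effect is probably small and its direction is not known. On the stated assumptions the exclusion shifts the hypotension difference by about +0.10 to −0.31 points, and by nothing if never-infused patients carry the average risk. The time origin adds about −0.02 to −0.10 points for the usual gap. Both ranges rest on an assumed hypotension rate; the first also rests on assumed values for the never-infused share and risk, and the second on even onset over 48 to 120 hours.

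Nothing here reaches efficacy: the primary analysis and death through Day 30 use the FAS and count from randomization. Severity: minor.

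**What to change.** 1. Make the safety-set definition and Tables 3-1 and 3-2 agree, including DRUG14 if it also marks the safety set. One way is to keep the as-treated tables to serelaxin recipients versus SOC-randomized patients who did not receive it. State explicitly that never-infused serelaxin patients are not counted in the SOC column.
2. Add one supplementary adverse-event and serious-adverse-event table, including the hypotension safety risk, in FAS patients with a post-baseline safety assessment. Present it by randomized arm, counted from randomization in both arms, with never-infused patients kept and their number shown.
3. As a minor clarification, say whether the safety-risk tables in SAP 5.3 are treatment-emergent only. The adverse-event text there reports safety risks for treatment-emergent events, and the later safety-risk paragraph does not repeat the restriction.

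The cost is SAP wording and one extra table set. No new data are needed: randomization time, event start date and time, and Day 30 follow-up of untreated patients are already collected. The downside is slight dilution in the added table. At 0.5%–2% never infused, a true drug excess shrinks by 0.5%–2% of its size, so the table supplements the as-treated tables and does not replace them.

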4. VARIABLES

4.1. EFFICACY PARAMETERS

Primary efficacy parameter

Worsening of Heart Failure/all cause death through Day 5

The primary efficacy variable of the study is the time to in-hospital Worsening of Heart Failure (WHF) requiring rescue therapy or all cause death through Day 5 post randomization.

In-hospital WHF through Day 5 post randomization includes worsening signs and/or symptoms of heart failure that require an intensification of intravenous therapy for heart failure or mechanical ventilation, renal or circulatory support. Such treatment can include the institution or uptitration of IV furosemide, IV nitrates or any other IV medication for heart failure, or institution of mechanical support such as assisted (invasive or non-invasive) ventilation, ultrafiltration, haemodialysis, intra-aortic balloon pump or ventricular assist device, etc. This endpoint also includes patients who die in this 5-day period of any cause before experiencing episode(s) of WHF.

A central event adjudication committee is appointed to oversee the WHF primary endpoint adjudication.

Relevant evaluations to detect in-hospital WHF are performed in the serelaxin arm at 6, 12, 24 and 48 hours from start of study drug infusion, daily through index hospitalization, at Day 5 and discharge, and then at Day 14. For patients in the SOC arm, relevant evaluations are performed at 6, 12, 24 and 48 hours from randomization, daily through index hospitalization, at Day 5 and discharge, and then at Day 14.

Death information is collected in a dedicated eCRF section.

Secondary efficacy parameters

In-hospital Worsening of Heart Failure/all cause death/hospital readmission for HF through Day 14

The secondary efficacy endpoint is time to worsening HF requiring rescue therapy as defined above, or all cause death, or hospital readmission for heart failure through Day 14 post randomization.

	Statistical Analysis Plan
	Sponsor: NOVARTIS Protocol number: CRLX030A3301

Relevant evaluations to detect in-hospital WHF are performed in the serelaxin arm at 6, 12, 24 and 48 hours from start of study drug infusion, daily through index hospitalization, at Day 5 and discharge, and then at Day 14. For patients in the SOC arm, relevant evaluations are performed at 6, 12, 24 and 48 hours from randomization, daily through index hospitalization, at Day 5 and discharge, and then at Day 14.

Death and re-hospitalization information are collected in dedicated eCRF sections.

Persistent signs and symptoms of HF/non-improvement

The number of patients with persistent symptoms or signs of HF / not showing an improvement versus baseline conditions through Day 5 (persisting need of IV therapy for HF) will be evaluated.

Patients with persistent symptoms or signs of HF / not showing an improvement versus baseline conditions through Day 5 are those patients who take any IV therapy for HF at each assessment time point as reported in the eCRF sections “IV Loop Diuretic Medication for Heart Failure” and “IV Medications Other than Loop Diuretics”.

Moreover, the investigator or appropriate qualified designee evaluates the symptoms and signs of heart failure, including dyspnea on exertion or at rest, orthopnea, rales, jugular venous pulse (JVP) and peripheral edema. These evaluations are performed at baseline, 6, 12, 24 and 48 hours from start of study drug infusion, daily through index hospitalization, at Day 5, at discharge and then at Day 14 for the serelaxin arm. For patients in the SOC arm, relevant evaluations are performed at baseline, at 6, 12, 24 and 48 hours from randomization, daily through index hospitalization, at Day 5, at discharge, and then at Day 14.

These evaluations should be done at approximately the same time of the day, each day, in the same position and hospital/clinic setting, preferably by the same assessor.

Renal deterioration

Renal deterioration is defined as an increase of ≥ 0.3 mg/dL from screening in serum creatinine levels. Rate of renal deterioration at 24 hours, at 48 hours, at Day 5, at discharge, and at Day 14 post randomization will be evaluated.

Serum creatinine evaluations are performed locally at screening, at 24 and 48 hours, at Day 5, at discharge, and then at Day 14 post randomization.

Index length of hospital stay

Index length of hospital stay (in hours) is defined as the index hospitalization discharge date and time minus the index hospitalization admission date and time + 1 minute.

Index length of hospital stay, from admission to discharge, will be evaluated by location (emergency ward, emergency care unit, etc.).

Index hospitalization details are collected in eCRF at Screening, Day 5, discharge visit, Day 14 and Day 30 post randomization.

	Statistical Analysis Plan
	Sponsor: NOVARTIS Protocol number: CRLX030A3301

Death through Day 30

All deaths (adjudicated or not) occurring from randomization through Day 30 will be used in the analysis.

Re-hospitalization post-discharge

The number of re-hospitalizations per patient post-discharge will be described.

The time to first re-hospitalization (in days) will be defined as the first re-hospitalization admission date minus the randomization date + 1 day.

Health-related Quality of Life

The EQ-5D-5L is a widely used, self-administered questionnaire designed to assess health status in adults. The measure is divided into two distinct sections. The first section includes one item addressing each of five dimensions (mobility, self-care, usual activity, pain/discomfort, and anxiety/depression). The second section of the questionnaire measures self-rated (global) health status utilizing a vertically oriented visual analogue scale where 100 represents the “best possible health state” and 0 represents the “worst possible health state”.

In this study, the first administration of the EQ-5D-5L questionnaire occurs at baseline visit. If, for whatever reason, the patient is not able to fill in the questionnaire at baseline, it is possible to collect retrospectively these data on Day 2. If this is the case, on Day 2, two questionnaires need to be filled in at this visit: the first one asking the patient to retrospectively describe how he/she felt on the day of admission, and the second one asking the patient to describe how he/she feels today. A special permission was provided by EuroQoL for the use with 2-day recall of the questionnaire.

The EQ-5D-5L quality of life assessment is completed by all study patients (both serelaxin and SOC groups) at baseline (i.e., randomization), at Day 2, at Day 5, at discharge, and at Day 14 post randomization.

Resource utilization

Analyses will be undertaken, as appropriate, to assess the effects of treatments on healthcare resource utilization (RU) parameters.

Throughout the index hospitalization, the level of healthcare resource utilization shall be assessed by the overall length of stay, length of time in specific inpatient care units and procedures rendered during hospital stay. In addition, number of re-hospitalizations (events), number of patients with 1, 2, 3 re-hospitalization(s) and time to first (and recurrent) re-hospitalization(s) (in days) will be evaluated.

Moreover, the details about emergency/urgent care >24 hours not resulting in admission, including tests performed, will be provided.

Data for a health economic analysis are collected from eCRFs, most notably Hospital Discharge, Re-hospitalization and Death. Data on emergency/urgent care >24 hours not resulting in admission are collected in dedicated eCRF sections. Data on medical resource use are collected

	<h2>Statistical Analysis Plan</h2> 
Sponsor: NOVARTIS Protocol number: CRLX030A3301

--	---

for all enrolled patients from the index hospitalization at Day 5, at discharge, and then at Day 14, and through phone contact at Day 30 post randomization.

[REDACTED]

[REDACTED]

[REDACTED]

[REDACTED]

[REDACTED]

[REDACTED]

[REDACTED]

